Despite the potential effectiveness of cinacalcet to manage SHPT, tolerance of cinacalcet may be limited. RCTs show a 7-fold increased risk of hypocalcemia (RR=6.98; 95% CI: 5.10-9.53) (Ballinger *et al*, 2014; Sekercioglu *et al*, 2016). Similar to RCTs, hypocalcemia is commonly observed in patients treated with cinacalcet in observational studies (Kilpatrick *et al*, 2013; St Peter *et al*, 2009). Although cinacalcet is effective in reducing calcium and PTH, the rate of hypocalcemia events increased by five-fold from baseline (2.3% to 10.1%). In another study of over 7600 patients initiating cinacalcet from a large dialysis provider in the US, low calcium levels at baseline have been found to be predictive of cinacalcet discontinuation, however, hypocalcemia prior to discontinuation of cinacalcet did not appear to be a factor in the decision to reinstate use of cinacalcet (Kilpatrick *et al*, 2013). Its unclear how these hypocalcemia events may impact real-life cinacalcet utilization patterns and SHPT control.

In reponse to the development of cinacalcet-induced hypocalcemia (total calcium <8.4 mg/dl and >7.5 mg/dl), the Summary of Product Characteristics (SmPC) recommends clinicians to adjust calcium-containing phosphate binders, vitamin D sterols, dialysate calcium to raise serum calcium according their own clinical judgement (e.g. initiate, reduce or discontinue therapies); or if the patient has severe hypocalcemia (≤ 7.5 mg/dl), they are recommended to discontinue use until serum calcium levels are raised to levels of 8.0 mg/dl and symptoms have been resolved. Currently, there are limited data on the effectiveness of treatment interventions to manage cinacalcet-induced hypocalcemia and its impact on SHPT control. One observational study in the US found that 50% of patients who initiated cinacalcet experienced a hypocalcemia event (total calcium <8.4 mg/dL) (Brunelli *et al*, 2015). The proportion of patients who received at least one treatment intervention was directly related to increased severity of hypocalcemia: calcium <8.0-8.3 mg/dL (48.6%), 7.5-7.9 mg/dL (52.2%) and <7.5 (63.5%). The most common treatment intervention for low calcium was addition or up-titration of vitamin D

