9.2.2 Subject/Patient/Healthcare Professional Eligibility

9.2.2.1 Inclusion/Exclusion Criteria

Inclusion criteria

HD patients in AROii cohort i) aged ≥ 18 , ii) filled a cinacalcet prescription after 01 January 2007, iii) enrolled in AROii for at least 90 days prior to cinacalcet initiation and have at least 90 days follow-up following cinacalcet initiation (*Cohort A*). HD patients who have serum Ca ≥ 8.4 mg/dL at time of cinacalcet initiation will be included in subsequent analyses (*Cohort B*). A sub-set of HD patients who develop hypocalcemia (serum Ca < 8.4 mg/dL) will define *Cohort 1* which will be used to evaluate the primary objectives. HD patients with hypocalcemia who discontinued cinacalcet will be included in further sub-analyses (*Cohort C*).

Exclusion criteria

Patients with i) parathyroidectomy up to and including the first 90 days of follow-up, ii) a prescription for cinacalcet is less than 15 days (2 weeks) with no further prescriptions

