9.2.4.1 Censoring

Patients will begin to accrue time at risk from the end of their relevant baseline period until they experienced hypocalcemia (*Cohort B*), discontinued cinacalcet (*Cohort 1*) or reinitiated cinacalcet (*Cohort C*). Patients will also be censored if they died, underwent parathyroidectomy or a renal transplant, or were lost to follow-up during the respective follow-up periods. Patients will be considered lost to follow-up if they left a dialysis facility for any reason and did not return to the same or another FMC facility within 45 days.

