9.3.2.1 Incidence of hypocalcemia

The cumulative incidence of first hypocalcemia event (# of new cases with serum calcium value <8.4 mg/dL) will be calculated overall and stratified by mutually exclusive groups of mild (≥ 8.0 - < 8.4 mg/dL), moderate (≥ 7.5 - < 8.0 mg/dL), and severe (< 7.5 mg/dL).

The time period will be monthly following cinacalcet initiation. Patients are at risk for each specified time period if they have an active supply of cinacalcet and therefore at risk of hypocalcemia. Patients are not at-risk if they do not have an active supply of cinacalcet, died, had a parathyroidectomy or a renal transplant, or was lost to follow-up during the specified time period.

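### The monthly risk set in 9.3.2.1 is fixed by exits during the same month, whatever their order relative to hypocalcemia, and this conflicts with the censoring rule in 9.2.4.1

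*Protocol*

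**What the plan says.** Protocol 9.3.2.1 sets the interval: "The time period will be monthly following cinacalcet initiation". It gives one condition for being in the risk set: "Patients are at risk for each specified time period if they have an active supply of cinacalcet and therefore at risk of hypocalcemia". It then lists what takes a patient out: "Patients are not at-risk if they do not have an active supply of cinacalcet, died, had a parathyroidectomy or a renal transplant". The list closes with one more reason, which names the month itself as the window: "or was lost to follow-up during the specified time period". The section does not say at which point of the month supply is judged. It also does not say what happens to a low calcium value recorded before the exit.

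Protocol 9.2.4.1 treats Cohort B differently: "Patients will begin to accrue time at risk from the end of their relevant baseline period until they experienced hypocalcemia". Death, parathyroidectomy, transplant and loss are reasons for censoring there. Running out of cinacalcet is not mentioned. Section 9.6.2.3 refers to 9.2.4.1 for censoring in the Cox analysis of time to first hypocalcemia.

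Two further statements limit or drive the effect:

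- Entry under 9.2.2.1 requires that patients "have at least 90 days follow-up following cinacalcet initiation", and excludes "parathyroidectomy up to and including the first 90 days of follow-up".
- On severe hypocalcemia, 7.1 reports from the product label that "they are recommended to discontinue use until serum calcium levels are raised to levels of 8.0 mg/dl".

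**The concern.** A risk set should be known at the start of the interval. Here membership depends on what happens before the interval ends. Take a patient with a calcium below 8.4 mg/dL on day 5 of a month who dies or is lost on day 20. Under 9.2.4.1 this patient is a case, and the later exit is irrelevant. Under the literal wording of 9.3.2.1 the patient is not at risk for that month, and nothing protects the earlier event. The patient has left by the next month, so the event is not picked up later.

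If exit were unrelated to calcium, this would be mainly untidy. It matters more for supply, because stopping cinacalcet is a recommended response to severe hypocalcemia. The condition that removes the patient can then be a consequence of the outcome being counted. At stake is the secondary cumulative incidence (objective 8.2.1), overall and by severity. So is its consistency with time to first event (8.2.3), which describes the same outcome in the same cohort.

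**Working it through.** **The two rules side by side (Cohort B, first hypocalcemia)**

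| | 9.3.2.1 | 9.2.4.1 |
|---|---|---|
| Time scale | monthly intervals | time from end of baseline |
| Exit after the event, same month | not at risk that month, order ignored | irrelevant, time at risk already ended |
| Death, parathyroidectomy, transplant, loss | removes the month | censors |
| End of supply | not at risk | not mentioned |

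The protocol does not say which rule governs the incidence estimate.

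**Planning figures (9.5).** 1245 × 0.47 = 585, stated as about 600. Half width = 1.96 × √(0.25/600) = 0.040. Both reproduce. No figure is stated for the at-risk rule, so what follows is illustration.

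**Step 1: background exits.** From 9.2, (10,600 − 1,876)/33,000 = 0.264 exits per person-year. This is the whole AROii cohort, not cinacalcet initiators. An event uniform within the month leaves on average half a month: 0.264/24 = 1.1% of events followed by an exit in the same month. The entry rules prevent death, loss and parathyroidectomy from acting in about months 1–3. With a constant hazard reaching 47% at 12 months, 1 − 0.53^0.25 = 14.7% have had the event by month 3. So 1 − 14.7/47 = 69% of events come later, and 1.1% × 0.69 = 0.76%.

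**Step 2: stopping cinacalcet, if a lapse within the month removes the patient.** Assumptions: event uniform over 30 days; delay to stopping exponential with mean m days (not in the protocol); 17% stop (US observational figure in 7.2).

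P(same month) = 1 − (m/30)(1 − e^(−30/m))

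| m | P(same month) | × 0.17 = events dropped | of 585 |
|---|---|---|---|
| 7 | 0.77 | 13.1% | 77 |
| 14 | 0.59 | 10.0% | 58 |
| 30 | 0.37 | 6.3% | 37 |

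Section 7.2 also cites two trials in which under 1% of asymptomatic hypocalcemic patients were withdrawn. With 1%, the share dropped is at most 0.77 × 1% = 0.8%.

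**Step 3: effect on 12-month incidence.** Let h = 1 − 0.53^(1/12) = 0.0515 be the monthly risk. Let q be the share of cases, and d the share of non-cases, removed in a month. Dropping removed patients from numerator and denominator gives

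h′ = h(1 − q)/(1 − hq − (1 − h)d), and incidence 1 − (1 − h′)^12.

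| q | d = 0 | d = 2% | d = 5% |
|---|---|---|---|
| 2% | 46.3% | 47.0% | 48.0% |
| 6.3% (m = 30) | 44.9% | 45.6% | 46.6% |
| 10.0% (m = 14) | 43.6% | 44.2% | 45.2% |
| 13.1% (m = 7) | 42.5% | 43.2% | 44.1% |

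The reference is 47.0%, which is also what is obtained if every event preceding an exit is counted. The values of d, and q = 2%, are assumptions. Incidence falls when q > d, is unchanged when q = d, and rises when q < d.

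For background exits unrelated to calcium, non-cases are exposed for the whole month (0.264/12 = 2.2%) and cases for half of it (1.1%). The result is 47.4%, slightly upward. With q = 1.1% and d = 0 it is 46.6%.

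**The case against.** The strongest reply is that 9.3.2.1 never says an observed case is deleted. It defines the numerator separately, as new cases with calcium below 8.4 mg/dL, and the at-risk sentences can be read as describing the denominator only. The phrase about the period stands next to loss to follow-up. Death, parathyroidectomy and transplant could mean exits that had already happened when the month is assessed, the usual life-table sense. A patient supplied on the test date also meets the condition of having an active supply. Finally, 9.2.4.1 and 9.6.2.3 already treat exits correctly for time to event, and an analysis plan that is not shown may settle when in the month status is judged.

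Much of this stands. Loss of the event is an inference from literal wording, and for supply the wording is ambiguous. The 6–13% rests on assumed delays and on an unpublished US figure given without a time window. What does not stand is that 9.2.4.1 cures the problem. It is a different rule for the same outcome, it is silent on supply, and 9.3.2.1 does not refer to it. The protocol has stated a rule here, not left one open.

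A reader might infer two stronger things that the protocol does not support:

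- **That incidence is biased downward whatever the exit reason.** For death, transplant and loss, no reason is given why cases should exit more often than non-cases, and the calculation can go either way.
- **That Cohort 1, and with it the primary discontinuation rate, is distorted.** Sections 9.2.2.1 and 9.3.1.2 define Cohort 1 by developing a serum calcium below 8.4 mg/dL, without reference to the monthly risk sets.

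**Conclusion.** The rule is wrong as written, and the severity is minor. Section 9.3.2.1 makes a month's risk set depend on exits during that month without regard to order, and it contradicts 9.2.4.1 for the same cohort and outcome.

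The part due to death, loss and surgery is about 1% of events or fewer, with no established direction. The larger effect needs the reading in which a lapse of supply within the month removes the patient. On that reading the loss depends on the outcome. With 17% stopping and mean delays of 7–30 days it takes 6–13% of events, moving a 47% incidence to about 42.5–44.9% if non-cases are not removed, and by less if they are. Because 7.1 ties stopping to severe hypocalcemia, the severe stratum would probably be hit hardest, but the protocol gives no figure for that. The consequence shown is confined to a secondary descriptive objective.

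**What to change.** In 9.3.2.1:

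- Set at-risk status at the start of each month, or estimate cumulative incidence in continuous time.
- Count a first calcium below 8.4 mg/dL as an event if its test date precedes the exit or end-of-supply date.
- Let patients who exit contribute up to the exit date.

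Then align 9.3.2.1 with 9.2.4.1 and state in both whether end of supply censors, so that incidence and time to first event use the same risk set. The cost is a few sentences and date-based programming; prescription dates are already captured, and no new data are needed.

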9.3.2.2 Frequency of hypocalcemia

The frequency of hypocalcemia events will be calculated as the total number of consecutive serum calcium values below 8.4 mg/dL during 12 months following cinacalcet initiation. Patients with less than 12 months follow-up will be excluded from this specific analysis.

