5. To explore the impact of hypocalcemia treatment on serum calcium level
6. To explore the impact of hypocalcemia on cardiovascular (CV) events or death

- **Hypothesis(es)/Estimation**

No formal hypothesis will be tested.

- **Study Design/Type**

A retrospective cohort study using electronic medical records of HD patients prescribed cinacalcet in Europe

- **Study Population or Data Resource**

The source population for this study is the AROii cohort, which comprises adult subjects presenting at one of 304 participating FMC facilities in 14 European countries enrolled between 01 January 2007 and 31 December 2009. AROii data collection covers until the end of 2014 will reflect current practice patterns. Patients are chronic (ten or more contiguous dialysis sessions) incident (<183 days since commencing renal replacement therapy (RRT)) HD patients with no history of renal transplantation or peritoneal dialysis.

- **Eligibility Criteria**

Inclusion criteria: HD patients in AROii cohort i) aged ≥ 18 , ii) filled a cinacalcet prescription after 01 January 2007, iii) enrolled in AROii for at least 90 days prior to cinacalcet initiation and have at least 90 days follow-up following cinacalcet initiation (*Cohort A*). HD patients who have serum Ca ≥ 8.4 mg/dL at time of cinacalcet initiation will be included in subsequent analyses (*Cohort B*). A sub-set of HD patients who develop hypocalcemia (serum Ca <8.4 mg/dL) will define *Cohort 1* which will be used to evaluate the primary objectives. HD patients with hypocalcemia who discontinued cinacalcet will be included in further sub-analyses (*Cohort C*).

Exclusion criteria: Patients with i) parathyroidectomy up to and including the first 90 days of follow-up, ii) a prescription for cinacalcet is less than 15 days (2 weeks) with no further prescriptions.

- **Follow-up**

Follow-up will commence on the date patients initiate a cinacalcet prescription and will continue for at least 90 days and up to 12 months. Among patients who develop hypocalcemia, follow-up will continue for 12 months. And among patients who discontinued cinacalcet, follow-up will continue for 12 months.

- **Variables**

- **Outcome Variables:** Incidence of hypocalcemia; frequency of hypocalcemia; time to first hypocalcemia event; time to any treatment intervention, rate of cinacalcet discontinuation; cinacalcet prescribing patterns; prescribing patterns for vitamin D, phosphate binders and CVD medications; time to cinacalcet re-

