8.2 Secondary objectives

HD patients with cinacalcet prescription and serum calcium >8.4 mg/dL at baseline

(Cohort B)

- 8.2.1 To determine the incidence of hypocalcemia in SHPT patients with CKD on HD following cinacalcet initiation
- 8.2.2 To determine the frequency of hypocalcemia events in cinacalcet patients
- 8.2.3 To determine time to first hypocalcemia event
- 8.2.4 To describe characteristics of cinacalcet patients who develop and who do not develop hypocalcemia
- 8.2.5 To identify factors associated with time to hypocalcemia event in cinacalcet patients

Hypocalcemia HD patients who discontinued cinacalcet prescription (Cohort C)

- 8.2.6 To determine time to cinacalcet re-initiation
- 8.2.7 To determine the rate of cinacalcet re-initiation among patients who discontinued cinacalcet following hypocalcemia event
- 8.2.8 To describe factors associated with time to cinacalcet re-initiation event in patients who discontinued cinacalcet following hypocalcemia event
- 8.2.9 To describe treatment patterns (e.g. vitamin D, phosphate binders and CVD medications) at time of hypocalcemia event, at time of discontinuation, and at time of cinacalcet re-initiation
- 8.2.10 To describe the trajectory of PTH, calcium and phosphate values following cinacalcet initiation, following hypocalcemia event, and following cinacalcet re-initiation

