9.2 Setting and Study Population

The source population for this study is the AROii cohort, which comprises of adult subjects presenting at one of 304 participating facilities in 14 European countries (*Czech Republic, France, Hungary, Ireland, Italy, Poland, Portugal, Romania, Russia, Serbia, Slovak Republic, Slovenia, Spain, and United Kingdom*) and Turkey enrolled between 01 January 2007 and 31 December 2009. Out of 10,600 patients enrolled, 1876 patients were still on follow-up by the end of 2014.

AROii, a closed-cohort by design, comprises of chronic (ten or more contiguous dialysis sessions) incident (<183 days since commencing renal replacement therapy (RRT)) haemodialysis patients with no history of renal transplantation or peritoneal dialysis. Data are captured electronically via the FMC European Clinical Database (EuCliD) and supplied on a quarterly basis. By Q4 2014, the AROii study population had accrued over 33,000 person-years of follow-up.

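### The hypocalcemia frequency analysis drops every Cohort B patient with under 12 months of follow-up, so it describes 12-month completers, not the cinacalcet patients named in objective 8.2.2

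*Protocol*

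**What the plan says.** Secondary objective 8.2.2, set in Cohort B, is: "To determine the frequency of hypocalcemia events in cinacalcet patients". Exploratory objective 8.3.3 asks for the same quantity by PTH level.

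Section 9.3.2.2 makes the outcome the "total number of consecutive serum calcium values below 8.4 mg/dL during 12 months following cinacalcet initiation", and then states: "Patients with less than 12 months follow-up will be excluded from this specific analysis".

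Three other places determine who that removes:

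- Section 9.2.2.1 admits patients to Cohort A, and so to Cohort B, if they "have at least 90 days follow-up following cinacalcet initiation". The abstract likewise says that follow-up "will continue for at least 90 days and up to 12 months".
- Section 9.2.4.1 says what ends follow-up early: "Patients will also be censored if they died, underwent parathyroidectomy or a renal transplant, or were lost to follow-up during the respective follow-up periods". Loss means that the patient "left a dialysis facility for any reason and did not return to the same or another FMC facility within 45 days".
- Section 9.2.1.1 closes the study period on 31 December 2014.

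**The concern.** A patient followed for between 90 days and 12 months belongs to Cohort B but not to the frequency analysis. Whether a patient is analysed depends on what happens after initiation. Parathyroidectomy and transplantation bear directly on PTH and calcium, and death and departure may well be related to them, so it is not safe to assume that those who leave have the same hypocalcemia frequency as those who stay.

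The estimate then does not answer objective 8.2.2, which refers to cinacalcet patients without a completion condition. If early exit differs by PTH level, the groups compared under 8.3.3 are also selected to different degrees.

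The protocol treats the same losses differently elsewhere. Section 9.3.2.1 takes such patients out of a monthly risk set for incidence, and sections 9.2.4.1 and 9.6.2.3 censor them in the time-to-event analyses. Only the frequency analysis discards the patient. Neither the sensitivity analyses (9.6.2.5) nor the limitations (9.8) mention this.

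**Working it through.** **The plan's own figure.** The only size calculation is in section 9.5. 0.47 × 1245 = 585, which the protocol rounds to about 600, and 1.96 × √(0.25/600) = 0.040. Both reproduce. They concern the discontinuation proportion in Cohort 1, so they say nothing about the frequency analysis, for which no figure is given.

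**Exit rate.** Section 9.2 states: "Out of 10,600 patients enrolled, 1876 patients were still on follow-up by the end of 2014", with over 33,000 person-years accrued.

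- Exits: 10,600 − 1,876 = 8,724.
- Crude rate: 8,724 / 33,000 = 0.264 per person-year. Because the denominator is given as more than 33,000, this is slightly high.
- It belongs to the whole AROii cohort. The rate in cinacalcet users is not in the protocol, so 0.10 to 0.30 per year is shown as an assumed range.

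**Share dropped.** Cohort B patients have already reached day 90, so the relevant window is 365 − 90 = 275 days. With a constant hazard h (assumption), d = 1 − exp(−h × 275/365). At h = 0.264 this is 1 − exp(−0.199) = 0.181.

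**Effect on the rate.** Let m be the mean follow-up in years of those who leave between day 90 and day 365, which follows from the same constant hazard. Let k be the leavers' event rate divided by the completers' rate (assumption). Relative to completers, the all-patient person-time rate is

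R = [(1 − d) + k·d·m] / [(1 − d) + d·m]

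and the completer-only figure is off by 1/R − 1. At h = 0.264 and k = 2: (0.819 + 2 × 0.181 × 0.611) / (0.819 + 0.181 × 0.611) = 1.040 / 0.930 = 1.119, so the error is −11%.

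| h per year | dropped, d | of 1245 users | m | error, k = 0.5 | k = 1 | k = 2 |
|---|---|---|---|---|---|---|
| 0.10 | 7% | 90 | 0.62 | +2% | 0 | −4% |
| 0.264 | 18% | 225 | 0.61 | +6% | 0 | −11% |
| 0.30 | 20% | 252 | 0.61 | +7% | 0 | −12% |

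The counts use all 1245 users, before the Cohort A and B criteria, so they are rough upper figures.

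**Observed time discarded** at h = 0.264: 0.181 × 0.611 / 0.930 = 12% of person-time.

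**Administrative loss** comes on top. Patients who start cinacalcet in 2014 up to about 2 October (90 days before 31 December) can meet the 90-day criterion but cannot reach 12 months. Their number is not given.

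**The case against.** The strongest reply is that the rule is narrow. It covers one descriptive secondary outcome and, by inference, its PTH-stratified version; section 9.6.2.4 does not restate the exclusion for 8.3.3. No hypothesis is tested. The primary objectives use Cohort 1 and are untouched, and patients with short follow-up still count towards incidence and time to first event. A count in fully observed patients also gives everyone the same window. A pooled yearly rate does not: if events cluster soon after initiation, patients with short follow-up add mostly early, high-rate time. All of this stands. It limits the importance of the point and favours a mean cumulative count over a simple rate, but it does not make the completers the population named in 8.2.2.

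The size is also open to challenge. An exit rate for all incident dialysis patients is being applied to a narrower group, and no value of k comes from the protocol. That stands too, which is why a range is shown.

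A reader might infer more than the text supports:

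- *Everyone who died or left is dropped.* Only exits within 12 months of initiation count. A patient who stops cinacalcet but stays on dialysis at an FMC facility keeps follow-up and is retained.
- *About 23% are lost.* That is 1 − exp(−0.264), counted from initiation. Losses before day 90 come from the eligibility criterion, not from 9.3.2.2.
- *All 2014 starters are lost through this rule.* Those starting after about 2 October fail eligibility anyway. The others are cut off by the calendar, so they are not evidence of survivor selection.
- *Frequency and incidence cannot be read together because of this rule.* Incidence also requires an active cinacalcet supply, which frequency does not, so their denominators would differ even without the exclusion.

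**Conclusion.** The point holds for objective 8.2.2 and, through the shared definition, for 8.3.3. The exclusion is written into the protocol, selects on events after initiation, and is not repaired elsewhere in the document. The primary objectives and the incidence and time-to-event analyses are not affected.

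Under a constant hazard, the rule would drop roughly 7% to 20% of patients who reach day 90, and about 18% if cinacalcet users leave at the whole-cohort rate. The resulting error in the event rate depends on k, which is unknown. It is zero if leavers and completers have equal rates, about 4% to 12% too low if leavers have twice the rate, and about 6% too high at half the rate and 0.264 exits per year. The protocol does not support a claim about direction. This is a worthwhile, inexpensive correction to a secondary descriptive outcome, not a threat to the study's main results.

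**What to change.** Replace the exclusion sentence in 9.3.2.2 so that all Cohort B patients contribute their observed time up to 12 months. Report the mean cumulative count of hypocalcemia events by month since initiation, with death as a terminal event, overall and by PTH band. Events per patient-year from a negative binomial model with a log person-time offset would be an acceptable alternative. Keep the 12-month completer count as a sensitivity analysis.

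Two definitions must be settled in the same edit. The event unit is unclear, because the present wording does not say whether single low values or runs of consecutive low values are counted. Time at risk also needs stating, including whether it requires an active cinacalcet supply as the incidence outcome does.

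No new data are needed; the cost is a short rewrite and a standard analysis. The downside is a summary less simple than a count per patient. If the yearly rate is chosen, it also assumes a roughly constant event rate, which the mean cumulative count avoids.
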